7.13.2. CA-125

Serum CA-125 assessments will be performed within 14 days prior to the first dose of study drug, and at each radiologic tumor assessment (\pm 4 days) (Table 2). CA-125 should be assessed by the same laboratory throughout the study.

8. ASSESSMENT OF SAFETY

8.1. Recording Adverse Events and Serious Adverse Events

AEs, including those attributed to study procedures, will be documented in the clinical trial database and monitored continuously throughout the study from the time of informed consent until 30 days after the patient's last study treatment.

Document ID: CLIN-00067	Title: IMGN853-0419 Clinical Study Protocol	Version: 2.0
Legacy ID: 26587		Approved Date: 12/22/202

Only AEs/SAEs which are considered related to a study procedure (ie, blood draw or fresh tumor biopsy) will be captured during the pre-screening period, ie, from the time of signing of the pre-screening informed consent (if one is utilized) until the time of signing of the main study informed consent, or until the patient is determined to be a screen failure. All AEs and SAEs, regardless of causality, will be captured after the main study ICF has been signed.

SAEs will continue to be followed by ImmunoGen Pharmacovigilance until resolution, stabilization, or return to baseline. Beyond this defined reporting period, any unsolicited SAE assessed as related to the study drug by the Investigator and reported to ImmunoGen will be collected and processed. Additional information obtained after database lock, will reside solely in the safety database.

The Investigator should follow and provide updates for all AEs until clinical recovery is complete, laboratory values return to normal, the patient stabilizes, or death occurs, to ensure the safety of the patients. This may mean that observations continue beyond the last planned visit per protocol and that additional investigations may be requested by the Sponsor.

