Ophthalmic Exam ^k		• ^c	Every other cycle from time treatment-emergent eye disorder first reported			• ^k	• ^k	
Ocular Symptom Assessment ^l		• ^c	•	•	•	•	•	
Radiologic Tumor Assessment ^m		• ^a	Every 6 (±1) weeks from C1D1 for first 36 weeks, then every 12 (±3) weeks			• ⁿ	• ⁿ	
CA-125 ^o		• ^c	Collect at each radiologic tumor assessment (± 4 days)			• ⁿ	• ⁿ	
MIRV Administration			•	•	•			
Record AE/SAEs and Concomitant Medications ^p	• ^q	•	Collected continuously while patients are on study					
Blood Samples for Immunogenicity ^r			•	•	•	•	•	
Survival Phone Screen, Including New Anticancer Therapy ^s								•

Abbreviations: AE = adverse event; aPTT = activated partial thromboplastin time; BP = blood pressure; C = cycle; CA = cancer antigen; CT = computed tomography; CTCAE = Common Terminology Criteria for Adverse Events; D = day; ECG = electrocardiogram; ECOG PS = Eastern Cooperative Oncology Group; EOT = End of Treatment; FFPE = formalin-fixed paraffin-embedded; GCIC = Gynecologic Cancer Intergroup; INR = international normalized ratio; MIRV = mirvetuximab soravtansine MRI = magnetic resonance imaging; PD = progressive disease; PE = physical examination; PT = prothrombin time; RECIST = Response Evaluation Criteria in Solid Tumors; SAE = serious adverse event; WCBP = woman of childbearing potential

^a Must be within 28 days before C1D1 unless otherwise specified.

^b ECG assessment may be performed predose at C1D1 if not performed previously up to 28 days prior to first dose of MIRV.

Document ID: CLIN-00067	Title: IMGN853-0419 Clinical Study Protocol	Version: 2.0
Legacy ID: 26587		Approved Date: 12/22/2021

- ^c Must be within 14 days before C1D1.
- ^d Testing for FR α expression is required for all patients. All patients must submit tumor tissue block or fresh cut slides from available block (FFPE slides). Those who do not have archival tumor tissue to submit will be required to undergo procedures to obtain a new biopsy using a low-risk, medically routine procedure during the Pre-screening period to confirm eligibility. If the archival tumor tissue does not meet FR α criteria, a new biopsy tumor sample may be submitted and used to confirm this criterion.
- ^e Complete PE is required at Screening and the 30-Day Follow-up visit. At all other study visits while on MIRV, patients will have symptom-directed PEs.

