- ⁿ If a patient discontinues before documentation of PD, a tumor assessment and CA-125 will be assessed at the EOT or 30-Day Follow-up visit, if not performed within the previous 6 weeks. Tumor assessments and CA-125 will continue to be performed every 12 (\pm 3) weeks until PD is documented per RECIST v1.1 or the patient starts new anticancer therapy. Patients who discontinue MIRV for reasons other than PD will continue with tumor assessments until documentation of PD or the start of a new anticancer therapy, whichever comes first. Prior to Week 36 (from C1D1), assessments should occur every 6 weeks (\pm 1 week) as allowed by local requirements but must occur at an interval of no more than 12 weeks. After Week 36, assessment will occur every 12 weeks (\pm 3 weeks) until documentation of PD, death, the start of new anticancer therapy, or patient's withdrawal of consent (whichever occurs first).
- ^o CA-125 will be measured at the time of every tumor assessment (\pm 4 days) (responses will be confirmed according to GCIG criteria [Appendix C](#)).
- ^p All SAEs, and those AEs assessed by the Investigator as at least possibly related to study drug should continue to be followed until they resolve or stabilize, whichever comes first.

Document ID: CLIN-00067	Title: IMGN853-0419 Clinical Study Protocol	Version: 2 . 0
Legacy ID: 26587		Approved Date: 12/22/2021

^q Only AEs/SAEs which are considered related to a study procedure (ie, blood draw or fresh tumor biopsy) will be captured during the Pre-screening period, ie, from the time of signing the Pre-screening consent (if one is utilized) until the signing of the main study informed consent, or until the patient is determined to be a screen failure.

^r Immunogenicity will be assessed in samples collected prior to dosing (predose) on C1D1, C2D1, C3D1, C5D1, at EOT, and 30-Day Follow-up.

^s Survival follow-up assessments will occur every 3 months (± 1 month) until death, the patient is lost to follow-up or withdrawal of consent for survival follow-up, or EOS (whichever comes first). These assessments may be conducted by telephone. Information on the start of new anticancer therapy (including start date, therapy type/name, and response on treatment) should be collected. Additional survival follow-up calls may occur periodically if needed for regulatory requests or at time of database lock for either primary or final analysis.

Document ID: CLIN-00067	Title: IMGN853-0419 Clinical Study Protocol	Version: 2.0

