7. STUDY PROCEDURES

7.1. **Informed Consent**

Each patient will sign an Institutional Review Board (IRB)/Independent Ethics Committee (IEC)-approved ICF before any study-required procedures are conducted unless those procedures are performed as part of the patient's standard care ([Table 2](#)). Participants must be re-consented to the most current version of the ICF(s) per IRB/IEC guidelines during their participation in the study.

Patients will sign a pre-screening ICF to allow testing of fresh or archival tumor tissue by the assay required for study inclusion. If patients meet entry criteria for FR α positivity (high FR α) they will sign the main study ICF and proceed with remaining screening procedures per the Schedule of Assessments. In some cases, the pre-screening ICF and main study ICF may be merged into a single ICF based on site-specific guidelines or preference.

7.2. **Inclusion and Exclusion Criteria**

The inclusion and exclusion criteria are assessed during Screening (within 28 days before the first dose of MIRV on C1D1). All screening evaluations must be completed and reviewed to confirm that potential patients meet all eligibility criteria. The Investigator will maintain a screening log to record details of all participants screened and to confirm eligibility or record reasons for screening failure, as applicable. Procedures conducted as part of the patient's routine clinical management and obtained before signing an ICF may be utilized for screening or baseline purposes provided the procedure met the protocol-specified criteria and were performed within the timeframe defined in the Schedule of Assessments ([Table 2](#)). A patient is considered enrolled when they have received their first dose of MIRV ([Section 5.2.1](#)).

Document ID: CLIN-00067	Title: IMGN853-0419 Clinical Study Protocol	Version: 2.0
Legacy ID: 26587		Approved Date: 12/22/202

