12.1.2. Patient Information and Consent

An ICF that includes information about the study will be prepared and given to the patient. The ICF will contain all FDA and ICH required elements and be approved by an IRB/IEC. The ICF must be in a language understandable to the patient. Before enrolling in the clinical study, the nature, scope, and possible consequences of the clinical study will be explained to the patient in a form understandable to him or her. After the patient has been given ample time to read and ask questions regarding the ICF and has been informed that participation is voluntary, the patient must give consent in writing. If the patient is unable to read, oral presentation and explanation of the written ICF and information to be supplied must take place in the presence of an impartial witness. Consent must be confirmed orally and by the personally dated signature of the patient. The witness and the person conducting the informed consent discussions must also sign and personally date the informed consent document. The informed consent process must be recorded and dated in the patient's source document.

A copy of the signed and dated consent document(s) must be given to the patient. The original signed and dated consent document will be retained by the Investigator. Patient confidentiality will be maintained as outlined in [Section 12.3](#).

The Investigator must not undertake any measures specifically required solely for the clinical study until valid informed consent has been obtained.

A model of the pre-screening and the main study ICF will be provided to the sites separately for this protocol. The main study consent can be used to confirm a patient's consent to all study procedures and all study-specific screening tests. The pre-screening ICF can be used to pre-screen patients for FR α status via tumor FR α levels and soluble FR α levels in blood. If a patient is eligible based on FR α expression level, the patient will be provided the main study

Document ID: CLIN-00067	Title: IMGN853-0419 Clinical Study Protocol	Version: 2.0
Legacy ID: 26587		Approved Date: 12/22/202

consent and only after signing the main study ICF will additional study-specific screening tests be performed. Alternatively, the patient can be consented on both pre-screening and main study ICF at the same time; and FR α testing and study-specific screening assessments can be carried out in parallel.

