7.2.1. Fresh Biopsy Patient Adverse Events

Summary of adverse events, not necessarily TEAEs, experienced within 7 days of fresh biopsy will be generated by SOC, PT, and CTCAE grade. A listing of AEs experienced within 7 days of biopsy will also be generated for patients who have undergone fresh biopsy.

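### The 7-day fresh-biopsy AE summary in SAP 7.2.1 pools events collected under two capture rules, so the unrelated AEs in it depend on the consent route

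*Protocol*

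**What the plan says.** Protocol 8.1 sets two rules for AE collection. Before the main consent: "Only AEs/SAEs which are considered related to a study procedure (ie, blood draw or fresh tumor biopsy) will be captured during the pre-screening period". That period runs "from the time of signing of the pre-screening informed consent (if one is utilized) until the time of signing of the main study informed consent". It ends earlier if the patient is declared a screen failure. Afterwards: "All AEs and SAEs, regardless of causality, will be captured after the main study ICF has been signed". The restriction is repeated in Protocol 8.1.1.1 and 8.2.1 and in Table 2 footnote q, so it is deliberate.

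The consent route is flexible. Protocol 7.1 says that in some cases "the pre-screening ICF and main study ICF may be merged into a single ICF based on site-specific guidelines or preference". Protocol 12.1.2 describes the sequential route, with the main form signed after the FRα result, and then adds: "Alternatively, the patient can be consented on both pre-screening and main study ICF at the same time".

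The biopsy falls early. Under Table 2 footnote d, patients without archival tissue must "undergo procedures to obtain a new biopsy using a low-risk, medically routine procedure during the Pre-screening period to confirm eligibility".

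SAP 7.2.1 then plans: "Summary of adverse events, not necessarily TEAEs, experienced within 7 days of fresh biopsy will be generated by SOC, PT, and CTCAE grade". It adds a listing for the same patients. It does not filter by relatedness, split by consent route or name a population. SAP Section 9, which records departures from the protocol, mentions only the timing of the ORR analysis.

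**The concern.** A summary of AEs in a fixed window after a procedure is readable only if the same class of event was collected from every patient for the whole window. That does not hold here. A patient on a separate pre-screening form who has an unrelated AE three days after biopsy contributes nothing, because the event is not collected. A patient on a merged form with the same event contributes a row. Which rule applies is settled by site preference or by the timing of a signature, neither of which bears on the risk of the biopsy.

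At stake is the meaning of one descriptive table. A reader could take its any-AE line as an all-cause rate, which would be too low wherever capture was restricted. Or a reader could take it as a procedure-related rate, which would be too high wherever capture was full.

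**Working it through.** The plan states no figure to reproduce, so the check is a comparison of the texts.

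**Step 1. Which rule covers the 7 days after biopsy?**

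| Consent route | Procedure-related AEs | Unrelated AEs |
|---|---|---|
| Separate forms, main ICF signed after day 7 | collected | not collected |
| Separate forms, main ICF signed within the 7 days | collected | collected only from signature |
| Merged form, or both forms signed together before biopsy | collected | collected throughout |

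The last row rests on the natural reading of Protocol 8.1: the restricted period exists only where a separate pre-screening consent is used. The middle row needs the FRα result and the main signature within 7 days of biopsy. No turnaround time is given, so its frequency is unknown.

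**Step 2. What does SAP 7.2.1 count?** It counts every recorded AE in the window. The related column is uniform across routes and the unrelated column is not, so their sum is not uniform.

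**Step 3. Can the size be computed?** Let a be the 7-day risk of a procedure-related AE, b the risk of an unrelated AE (taken as independent of a), and m the share of biopsied patients under full capture for the whole window. Ignoring the middle row of the table, the expected any-AE proportion is

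a + (1 − a) × b × m.

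The first term does not involve m; the second is the part that depends on consent. Moving m from 0 to 1 changes the proportion by (1 − a) × b. The documents give none of a, b or m.

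Purely to show how the formula behaves, with assumed values:
- a = 10%, b = 20%: m = 0 gives 10.0%; m = 0.5 gives 10% + 0.9 × 20% × 0.5 = 19.0%; m = 1 gives 10% + 0.9 × 20% = 28.0%.
- Over assumed a of 5% to 20% and b of 10% to 30%, the full swing runs from 0.80 × 10% = 8 points to 0.95 × 30% = 28.5 points.

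These outputs restate the inputs and are not estimates for this trial. Moving m across its whole range is also artificial, since the protocol presents merged and simultaneous consent as alternatives to the sequential route and gives no shares.

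**Step 4. Can the two classes be told apart later?** Protocol Table 10 grades relationship to study drug, and the SAP 7.2 related category means MIRV-related. On the other side, Protocol 8.1 requires a judgement of procedure-relatedness in pre-screening, and SAP 7.2 expects AEs attributed to study procedures to be entered on the AE CRF, including those before first dose. The CRF itself is not among the documents, so whether it holds a procedure-relatedness field for AEs after the main consent is unknown.

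**The case against.** The strongest reply is that the events that measure biopsy harm are complete by design: procedure-related AEs are collected under every route. This stands. A reader might infer that the table as a whole is an artefact of consent logistics, or that biopsy harm is under-recorded at sites with separate forms. The documents support neither; only the unrelated events vary.

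Second, the table is broken down by SOC, PT and grade and comes with a listing, so a reader can often recognise procedure-type events. The all-AE listing in SAP 7.2 carries onset dates, and SAP 5.1.1 lists an informed consent date, though not which consent. This helps with individual events but does not give the summary counts a single meaning.

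Third, a reader might infer that the two classes can never be separated after the fact. That would require knowing that the CRF lacks the field, which cannot be known here.

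Fourth, materiality is low. A fresh biopsy is required only where archival tissue is missing, is optional where archival tissue fails the FRα criteria, and must be low-risk. TEAEs start at first dose, after main consent. All of this stands and sets the severity.

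Finally, a window-based summary has the merit of not depending on attribution. That argues for keeping the unrelated AEs on display rather than dropping them.

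**Conclusion.** The inconsistency is real: followed exactly, the plan produces a table in which procedure-related AEs have one definition throughout while unrelated AEs are collected or not according to consent route. The pooled any-AE count should be read neither as all-cause nor as procedure-related. The size cannot be computed from the documents, and no percentage should be attached to it.

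Severity is minor. The table is descriptive, and ORR, the other efficacy endpoints and the TEAE tables do not depend on it. The conclusion assumes that a merged or simultaneous consent counts as signature of the main ICF, and that both routes are actually used among biopsied patients. If every such patient followed one route and no main ICF were signed inside the window, the problem would disappear.

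**What to change.** In SAP 7.2.1:

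- Make AEs that the Investigator attributed to the biopsy the main rows. This is the class collected under every route.
- Show other AEs within 7 days separately, flagged or split by onset before or after main-ICF signature.
- Add a footnote stating the capture rule.

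For AEs that are already captured, record procedure-relatedness on the AE CRF under both consent routes, if the CRF does not do so now. Do not extend capture to unrelated AEs before the main ICF; that would enlarge data collection and require a protocol change.

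SAP 2.1 allows the analyses to be modified before final database lock. The cost is slightly more programming, possibly one CRF completion note, and fewer events in the main rows. The split by onset needs the main-ICF date to be available.

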8.1.1. Definition of Adverse Events

8.1.1.1. Adverse Event

An AE is any noxious, pathologic, or unintended change in anatomical, physiologic, or metabolic function as indicated by physical signs, symptoms, or laboratory changes occurring in any phase of a clinical study, whether or not considered study drug-related. This includes an exacerbation of a pre-existing condition. AEs include:

- Worsening (change in nature, severity, or frequency) of conditions present at the onset of the study
- Intercurrent illnesses
- Drug interactions
- Events related to or possibly related to concomitant medications
- Abnormal laboratory values (this includes significant shifts from baseline within the range of normal that the Investigator considers to be clinically important)
- Clinically significant abnormalities in PE, vital signs, and weight

Note that PD should not be reported as an AE unless it is considered to be drug-related by the Investigator.

All AEs, including AEs attributed to study procedures, occurring from the time of study informed consent until 30 days after last study treatment must be reported in the clinical database, regardless of the severity or relationship to study drug. Only AEs which are considered related to a study procedure (ie, blood draw or fresh tumor biopsy) will be captured during the pre-screening period, ie, from the time of signing the pre-screening consent (if one is utilized) until the signing of the main study informed consent, or until the patient is determined to be a screen failure. The Investigator should treat patients with AEs appropriately and observe them at

Document ID: CLIN-00067	Title: IMGN853-0419 Clinical Study Protocol	Version: 2.0
Legacy ID: 26587		Approved Date: 12/22/202

suitable intervals until the events stabilize, return to baseline, or resolve. AEs may be discovered through observation or examination of the patient, questioning of the patient, complaint by the patient, or by abnormal clinical laboratory values.

In addition, AEs may also include laboratory values that become significantly out of range. Such abnormal laboratory values or test results constitute AEs if they induce clinical signs or symptoms, are considered clinically significant (eg, cause study drug discontinuation or constitutes in and of itself an SAE, or require therapy), and should be recorded in the clinical database under the signs, symptoms, or diagnosis associated with them. In the event of an out-of-range value, the laboratory test should be repeated until it returns to normal or baseline or can be explained and the patient's safety is not at risk.

8.1.1.2. Serious Adverse Event

An SAE is any AE occurring at any dose that results in any of the following outcomes:

- Death
- Is life-threatening
- Requires inpatient hospitalization
- Requires prolongation of existing hospitalization
- A persistent or significant disability or incapacity or substantial disruption of the ability to conduct normal life functions
- A congenital anomaly or birth defect
- Important medical events that may not result in death, be life-threatening, or require hospitalization may be considered an SAE when, based upon appropriate medical judgment, they may jeopardize the patient and may require medical or surgical intervention to prevent one of the outcomes listed in this definition. Examples of such medical events include allergic bronchospasm requiring intensive treatment in an emergency room or at home, blood dyscrasias or convulsions that do not result in inpatient hospitalization

Note that hospitalization is defined as admission to treat a clinical AE. The following events would not be considered hospitalizations for SAE reporting purposes: 23-hour hold for observation, admission to a hospice facility or nursing home, respite care, outpatient surgery, social admission (eg, a homeless patient) or admission not associated with a precipitating clinical AE (eg, elective or pre-planned surgery, or in-patient administration of subsequent chemotherapy, etc.).

8.1.1.3. Adverse Events of Special Interest

There are no AEs of special interest (serious or nonserious) associated with MIRV.

